Optimization of Adaptive Text Messages for Cancer Survivors II (OATS II)

Protocol Number: CC #224523

Protocol Version Number: 1.3

Protocol Version Date: 12-01-2023

Study Intervention: Adaptive 12-week text message intervention using reinforcement learning to increase whole grain and reduce refined grain intake

Principal Investigator

[name] [name]

University of California, San Francisco

Statistician

[name]

Revision History

Version 1.0	08-31-2022
Version 1.1	12-09-2022
Version 1.2	10-10-2023
Version 1.3	12-01-2023

Proprietary and Confidential

The information in this document is considered privileged and confidential and may not be disclosed to others except to the extent necessary to obtain Institutional Review Board approval and informed consent, or as required by federal and state laws. Persons to whom this information is disclosed should be informed that this information is privileged and confidential and that it should not be further disclosed.

Protocol Signature Page

1. I agree to follow this protocol version as approved by the Institutional Review Board (IRB).
2. I will conduct the study in accordance with Good Clinical Practices (ICH-GCP) and the applicable IRB, ethical, federal, state, and local regulatory requirements.
3. I certify that I, and the study staff, have received the required training to conduct this research protocol.
4. I agree to maintain adequate and accurate records in accordance with IRB policies and federal, state, and local laws and regulations.

UCSF Principal Investigator

Printed Name

Signature

Date

Abstract

Title	Optimization of Adaptive Text Messages for Cancer Survivors II (OATS II)
Study Description	This study aims to develop a continuously adaptive text message-based intervention using reinforcement learning, a type of artificial intelligence, to increase the proportion of grains consumed that are whole grains in a racially/ethnically diverse group of colorectal cancer (CRC) survivors.
Study Intervention	Adaptive 12-week text message intervention using reinforcement learning to increase whole grain and reduce refined grain intake
Study Population	Participants for this study will include up to 60 CRC survivors for the proof-of-concept single-arm trial
Primary Objective	To determine the intervention's feasibility and acceptability
Secondary Objectives	
 1. To estimate the effect of the intervention on the percent of grains that are whole 2. To estimate the effect of the intervention on total fiber intake (g/d)
Recruitment Methods	Participants will be recruited through MyChart messages and letters from the UCSF CTSI Participant Recruitment Program, as well as clinician referrals at the University of California, San Francisco (UCSF) Helen Diller Family Comprehensive Cancer Center (HDFCCC) and the Zuckerberg San Francisco General (ZSFG) hospital.
Sample Size	Participants for this study will include up to 60 CRC survivors for the proof-of-concept single-arm trial
Duration of Study Participation	12 weeks
Unique Aspects of this Study	This study is the first to develop a continuously adaptive text message-based intervention using reinforcement learning, a type of artificial intelligence, to increase the proportion of grains consumed that are whole grains in a racially/ethnically diverse group of CRC survivors.

List of Abbreviations

AE	adverse event
BCT	behavior change technique
COM-B	Capability Opportunity Motivation – Behavior
CRC	colorectal cancer
CRF	case report form
CTCAE	Common Terminology Criteria for Adverse Events
CTMS	Clinical Trial Management System
DSMC	Data and Safety Monitoring Committee
DSMP	Data and Safety Monitoring Plan
GCP	Good Clinical Practice
HDFCCC	Helen Diller Family Comprehensive Cancer Center
HIPAA	Health Insurance Portability and Accountability Act
ICF	informed consent form
ICH	International Conference on Harmonization
IRB	Institutional Review Board
PRMC	Protocol Review and Monitoring Committee (UCSF)
RL	reinforcement learning
ZSFG	Zuckerberg San Francisco General

Table of Contents

Protocol Signature Page	2
Abstract	3
List of Abbreviations	4
Table of Contents	5
1 Introduction	7
1.1 Background on Dietary Interventions for Colorectal Cancer	7
1.2 Background on Text Messaging as a Behavioral Intervention in Diverse Populations.....	7
1.3 Study Rationale.....	8
1.4 Innovation	8
1.5 Risks/Benefits.....	8
2 Study Objectives and Endpoints.....	9
2.1 Primary Objective	9
2.2 Secondary Objectives	10
2.3 Exploratory Objective.....	10
3 Study Design	10
3.1 Schema	10
3.2 Characteristics	11
3.3 Sample Size.....	11
3.4 Primary Completion	11
3.5 Study Completion	11
4 Selection and Enrollment of Participants	11
4.1 Eligibility Criteria	11
4.2 Recruitment Methods	12
4.3 Inclusion and Recruitment of Women and Minorities	13

1.1 Background on Dietary Interventions for Colorectal Cancer

Dietary interventions are a promising approach for reducing colorectal cancer (CRC) mortality.¹⁻³ Guinter et al. reported that individuals with a low American Cancer Society (ACS) nutrition guideline score (based on intake of whole grains, fruits and vegetables, and red and processed meat) pre-diagnosis and high score post-diagnosis had a 29% lower risk of CRC-specific mortality versus patients with low scores at both time points.^{2,4} When examining the components in the ACS score among 992 stage III colon cancer patients, our team observed that those in the fourth quartile of proportion of grains that are whole had 35% lower risk of cancer recurrence and mortality compared to those in the first quartile (median % grains that were whole was 76% in 4th quartile vs. 11% in 1st quartile).^{1,4} An independent study of 1,575 people with stage I-III CRC reported that a 5-g/d increase in cereal fiber intake after diagnosis was associated with 33% lower risk of CRC-specific mortality.⁵ Overall, there is strong evidence that a high-fiber diet rich in whole grains lowers risk of CRC mortality.

Most CRC survivors do not achieve recommended intakes of whole grains or fiber.^{3,6,7} In a nationally representative sample of 1,550 cancer survivors, mean fiber intake was 15 g/d, half the 30 g/d recommended by the American Institute for Cancer Research.⁸ Moreover, differences in diet quality may play a role in CRC disparities. For example, on average in the United States (US), Black people have lower intake of grains compared to non-Latinx White people.⁹ Work from our team and others suggests that barriers to a high-fiber diet among cancer survivors include lack of time, energy, social support, access to healthy foods, and experience preparing high-fiber foods.¹⁰⁻¹⁵ While several dietary interventions have been developed for cancer survivors, past studies have largely tested resource-intensive, multi-component interventions in non-representative populations.¹⁶ These studies have observed changes in diet, but changes have often been small.¹⁷ Thus, more research is needed to develop dietary interventions for CRC survivors.

1.2 Background on Text Messaging as a Behavioral Intervention in Diverse Populations

Text messages are a promising tool for behavioral interventions in diverse populations. Nearly all adults in the US have mobile phones, and text messages are used by the majority of mobile phone users with little variation by race/ethnicity.^{18,19} Text messages do not require heavy data usage or high digital literacy, are inexpensive, and can be used to apply behavior change techniques (BCTs) such as information, instruction, feedback, prompts/cues, social support, self-monitoring, goal setting, and action planning.^{20,21} We and others have reported that text message-based interventions are feasible, acceptable and effective for dietary change.^{10,11,18,22} In fact, data suggest that stand-alone text messaging interventions could be as effective as blended interventions that combine text messaging with other tools (e.g., coaching) for less cost.¹⁸ Data are limited, however, in CRC survivors and people who identify with racial/ethnic minority groups.¹⁷ Moreover, patients consistently desire a more tailored experience in text message interventions and the optimal frequency, timing, and interactivity of text messages are not known.^{10,18,23}

Artificial intelligence solutions, including reinforcement learning (RL), may optimize digital health interventions in a scalable automated way. In 2019, Forman et al. reported on one of the first pilot studies to use RL in a weight loss intervention.²⁴ Their algorithm determined if participants would receive a coach call, a coach text message, or a non-tailored text message based on the frequency that participants self-monitored weight or diet, met calorie goals or physical activity goals, and weight loss. In a pilot study of 52 primarily White participants, the RL optimized intervention resulted in equal weight loss for half the cost of phone coaching. Yet, participants

desired more personalization, suggesting the need for message tailoring by individual characteristics and adaptation over time to account for behavior change and to maintain engagement.

1.3 Study Rationale

To address gaps and build on prior research, our team proposes to develop an adaptive text message-based dietary intervention for CRC survivors.²⁵ We will develop a RL algorithm to continuously adapt text message content and timing to increase whole grain and reduce refined grain intake. We plan to focus on CRC specifically because people with CRC have been under-represented in past behavioral intervention studies for cancer survivors, and the evidence for a role of diet after CRC diagnosis is strong.^{1,5,16} Additionally, experience from multiple studies suggests recruitment of people with CRC to clinical trials may require a more targeted approach than survivors of other common cancers.^{27,28}

1.4 Innovation

Past behavioral intervention trials have focused primarily on physical activity or weight loss.²⁹ Yet data suggest that diet is equally important for CRC survivors¹. Optimizing a behavioral intervention based on diet, which cannot be passively measured, is a particular challenge that we will address in this proposal. The results of this study will inform the design of a scalable intervention with broad reach that we will ultimately test in a randomized controlled trial. Enhancing CRC survivors' diet quality has potential to reduce CRC mortality and greatly improve public health.

1.5 Risks/Benefits

Potential Risks

The risks involved in this study are few. There is a minor risk of loss of confidentiality, either through the breach of data collected via the Internet or text messaging or through the breach of secure study databases, physical files, etc. Dietary modifications may result in changes in bowel function, including but not limited to diarrhea, constipation, increased urgency, flatulence, and/or bloating. These changes are not expected to be clinically significant but could impact quality of life if they occur.

Potential Benefit of the Proposed Research to Participants and Others

The benefits of healthy diet are well established. Intervention participants may experience decreases in symptom burden and improved physical functioning and quality of life. This study will produce societal benefit regarding knowledge about how to optimize a text message-based intervention to improve diet quality in cancer survivors. Given the minimal risk of study participation and potential benefits, the risks to participants are reasonable in relation to the anticipated benefits to society.

Procedures used to minimize risk

- Numerous studies have demonstrated that healthy diet is safe, feasible, and beneficial for cancer patients and survivors.
- Participants will receive tips on how to alleviate or avoid digestive changes due to increased whole grain and fiber intake.
- Participants will be asked to contact the study team at any time if they have questions or concerns about the study.

- All study files, folders, and records will be kept in locked file cabinets that can be accessed only by study personnel.
- All data will be exchanged over an SSL-protected connection, and all data will be encrypted.
- The study database and all survey data will be collected and stored in REDCap, the HealthySMS platform, Twilio, and UCSF's Research Analysis Environment (RAE), which have protections needed for storage of PHI.

Limited private identifiable information necessary for the conduct of the study will be collected in the proposed research project. For example: names, phone numbers, and email addresses. This information will be stored securely in REDCap, the HealthySMS platform, Twilio, and UCSF's Research Analysis Environment (RAE; mytransfer.ucsf.edu), which have the protections in place and approvals for the storage of PHI.

Importance of Knowledge to be Gained

Promotion of a healthy diet is an important aspect of cancer survivorship care. This research aims to create an intervention that can be remotely delivered and is appropriate for implementation on a large scale. We believe that the minimal risk involved with study participation are reasonable in relation to the knowledge that is expected to result.

2 Study Objectives and Endpoints

2.1 Primary Objective

Primary Objective	Endpoint(s)	Time Frame
Determine the intervention's feasibility ¹ and acceptability ²	
• Participants' responses to text messages that ask for a response• Participant surveys• Semi-structured end of study interviews	From 0 to 12 weeks

1) The intervention will be determined feasible if the median response proportion to text messages that ask for a reply is $\geq 70\%$, and the median score for the Feasibility of Intervention measure is ≥ 4 .

2) The intervention will be determined acceptable if median scores on the Acceptability of Intervention and Intervention Appropriateness Measures are ≥ 4 .

2.2 Secondary Objectives

Secondary Objectives	Endpoint(s)	Time Frame
1. Estimate the effect of the intervention on the percent of grains that are whole ¹	Change in percent grains that are whole, assessed via food frequency questionnaire	0 to 12 weeks
2. Estimate the effect of the intervention on total fiber intake (g/d)	Change in total daily fiber (g/d), assessed via food frequency questionnaire	0 to 12 weeks

¹ Percent of grains that are whole = servings per day of whole grains / (servings per day of refined grains + servings per day of whole grains)

2.3 Exploratory Objective

Exploratory Objective	Endpoint(s)
Assess convergence of the RL algorithm	Proportion of messages targeting capability, opportunity, or motivation sent during the 12-week period, overall and by sub-groups (e.g., race/ethnicity)

3 Study Design

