We will use the most up-to-date approaches for our RL model. For example, this may include a multi-armed bandit algorithm that predicts the outcome or "reward" (e.g., eating whole grains the previous day [yes/no], or servings of whole grains eaten on the previous day) based on action variables (e.g., whether to send a message, message type) and contextual variables (e.g., individual characteristics, whole grain intake yesterday/past week). RL algorithms "explore" what text messages to send by sending messages randomly at first and then "exploit" the information, so that over time, the algorithm sends more of the messages that predict more frequent intake of whole grains. In our proposal, participants' replies to daily text messages asking about their intake of whole grains on the previous day will be used as the "reward" data.

Participants' response rate to the daily question about whole grain intake is a primary outcome in this study. We will send a reminder message to participants who have not responded (e.g., "Please respond even if you ate 0 whole grains yesterday.") If participants do not respond a few days in a row, we will send a non-response message (e.g., "We haven't heard from you in a few days. Please respond to the text messages or contact our team at [study phone number].") If a participant does not respond for 7 consecutive days, we may invite them to a semi-structured

interview to understand reasons for non-response. Non-responders will continue to receive study text messages unless they request the messages be stopped (e.g., by texting back STOP or notifying the study team). All participants, including non-responders, will be asked to complete the surveys at 12 weeks to gather quantitative usability and acceptability data and estimate the effect of the intervention on diet behavior.

Educational material

At enrollment, all participants will receive printed materials defining the recommendations for whole grain intake, what is a whole grain, whole grain serving sizes, and cooking tips.

Intervention Components for Food Insecure Participants

We will use the Food Security module from the National Health Interview Survey to identify food insecure participants at enrollment. We will follow the standard of care at ZSFG for food insecure individuals: the study coordinator will provide a list of resources including food banks and meal delivery programs and facilitate application or SNAP benefits, if needed.

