9.2.3 Exploratory/Correlative Analysis

The RL algorithm will initially send messages from the three COM-B categories (capability, motivation, opportunity) or no message at random. If a category is predictive of subsequent higher whole grain intake or engagement (responses to text messages), the algorithm will begin to send that type of message more often. We will use one sample tests of proportions to explore if the proportion of text messages sent from each of the three COM-B categories or no message differs from 0.25. For example, for capability messages, our null hypothesis is that the proportion of messages targeting capability is equal to 0.25. The alternative hypothesis is that the proportion of messages targeting capability is not equal to 0.25.

We will also explore whether the distribution of text message type varies by sociodemographic factors (e.g., age, gender, race/ethnicity) using chi-square tests. For example, our null hypothesis is that the distribution of text message type is the same across racial/ethnic groups. The alternative hypothesis is that the distribution of text message type differs across racial/ethnic groups.

10 Study Management

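### The exploratory endpoint, a category share pooled over all 12 weeks, can show a departure from random sending but, at moderate values, not whether the algorithm converged

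*Combined protocol and SAP*

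**What the plan says.** The exploratory objective in section 2.3 is "Assess convergence of the RL algorithm". Its single endpoint is "Proportion of messages targeting capability, opportunity, or motivation sent during the 12-week period, overall and by sub-groups", with race/ethnicity as the example sub-group.

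Section 9.2.3 describes the start: "The RL algorithm will initially send messages from the three COM-B categories (capability, motivation, opportunity) or no message at random". It then plans a one-sample test of proportions for each option. For capability, "our null hypothesis is that the proportion of messages targeting capability is equal to 0.25", with a two-sided alternative. Chi-square tests compare the distribution of message type across sociodemographic groups.

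Section 5 (Study Intervention) gives the same picture of the algorithm, random at first and then learning, "so that over time, the algorithm sends more of the messages that predict more frequent intake of whole grains". It leaves the model open, but the inputs it mentions include "contextual variables (e.g., individual characteristics, whole grain intake yesterday/past week".

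Neither 2.3 nor 9.2.3 sets the random start apart, divides the 12 weeks, follows shares within a participant, or says what pattern would count as convergence.

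**The concern.** Convergence describes behaviour over time: the rule for choosing messages stops changing. The endpoint has no time axis, and two features of the planned algorithm make that matter.

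First, the random start is averaged with whatever follows, so the pooled share depends on how long the start lasted as well as on where the policy ended. Second, if messages are tailored, success may mean that different people settle on different categories, and those differences can cancel in the pooled share. Reporting by sub-group still pools people and weeks.

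This is the only planned measure of whether the algorithm settles. Adaptation is what the abstract presents as unique about the study, and section 1.4 says the results will inform the design of an intervention for a later randomised trial. A figure that cannot separate a settled policy from a moving one is of little use for that purpose.

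**Working it through.** **Inputs from the documents.** Up to 60 participants (3.3); 84 intervention days (6.1); four options, random at first, null value 0.25 (9.2.3). **Assumptions.** One category decision per participant per day (section 5 says 1-2 messages on most days), no dropout, and a test level of 0.05, since none is stated for this test. The length of the random start is not given, so it is varied.

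**The plan's figure.** Four equally likely options give 1/4 = 0.25, which reproduces the null when 'no message' counts as an option.

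**What the test detects.** Decisions: 60 × 84 = 5,040. SE = √(0.25 × 0.75 / 5,040) = 0.0061, and 1.96 × 0.0061 = 0.012. Treating decisions as independent, a share 1.2 percentage points from 0.25 is significant. That is a test of departure from random sending.

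**Dilution by the random start.** Suppose everyone moves to a stable 0.40 for one category after b random weeks. The pooled share is (b × 0.25 + (12 − b) × 0.40) / 12:

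| Random weeks | Pooled share |
|---|---|
| 1 | 0.388 |
| 2 | 0.375 |
| 4 | 0.350 |
| 6 | 0.325 |

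The end state is the same in each row.

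**Same share, different behaviour.**
- Settled: (4 × 0.25 + 8 × 0.50) / 12 = 0.417.
- Still moving: equal weekly steps from 0.25 in week 1 to 0.583 in week 12 average (0.25 + 0.583) / 2 = 0.417.
- Oscillating weekly between 0.25 and 0.583: also 0.417.

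Four-week blocks separate the first two. The settled policy gives 0.25, 0.50, 0.50. The climbing one, at 0.25 + (w − 1)/33 in week w, gives 0.295, 0.417, 0.538. The oscillating one gives 0.417 in every block and shows only in a weekly table.

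**Cancellation across people.** If a quarter of participants settle fully on each option after b random weeks, each option has share (b × 0.25 + (12 − b) × 0.25) / 12 = 0.25 for any b.

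A simulation illustrates this: 400 trials, Thompson sampling learning separately for each person, 14 random days, each option best for a quarter of people. With assumed reward rates of 0.9 for a person's best option and 0.2 otherwise, 99% of decisions in weeks 11-12 were the person's best option, pooled shares ranged from 0.238 to 0.262, and the 0.25 test never rejected. With 0.7 and 0.3, the late figure was 91% and the mean pooled share was again 0.25, although individual trials ranged from 0.215 to 0.283 and each test rejected in roughly 22-25% of them.

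**The reverse error.** With four equally good options, so nothing to learn, the same kind of algorithm made the test for a given category reject in about 95% of simulated trials when learning was shared across people, and in 50-57% when it was per person. Purely random sending gave about 5%. These rates depend on the assumed algorithm; the dilution and cancellation arithmetic does not.

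**The case against.** The analysis is labelled exploratory in a single-arm proof-of-concept trial whose success rests on feasibility and acceptability. Section 9.2.3 sets out only to explore whether shares differ from 0.25, and for that the test is apt. This stands, and it limits the weight of the point.

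The exact 0.25 result needs four equal sets, one of them settled on 'no message'. With an assumed 40/30/20/10 split and four random weeks, the leading share is (4 × 0.25 + 8 × 0.40) / 12 = 0.35, clearly off 0.25. That is fair, but 0.35 is also what results when nobody locks on and everyone drifts to 0.40, so the share still does not say which happened. If tailoring follows sociodemographic characteristics, the planned sub-group comparison could reveal it; tailoring on recent intake would not show there.

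Three stronger readings are tempting and are not supported:
- **The endpoint can never indicate convergence.** An extreme share would be suggestive: if everyone locks onto one category after two random weeks, it is (2 × 0.25 + 10 × 1) / 12 = 0.875.
- **Sub-group differences will arise from enrolment order.** This needs learning shared across participants and sub-groups that enrol at different times. Section 5 states its model and context variables only as possibilities, and nothing says race/ethnicity will track enrolment order.
- **The 0.25 null is wrong and guarantees a false finding.** Among messages sent, random four-way sending gives 1/3 per category, and section 2.3 read alone suggests that denominator. But 9.2.3 lists 'no message' as a fourth option and sets 0.25 on that basis. The two sections need aligning; a false result does not follow.

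**Conclusion.** The point holds in limited form. The endpoint does not measure the objective it is attached to: it can show that sending departed from random, and an extreme value would hint at convergence, but moderate values have no clear reading. Settled and unsettled policies can share a pooled figure (0.417 in the example), and full personal convergence can leave it at 0.25.

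Pooling across people is inferred from the word overall in 2.3 and from the one-sample test; no per-participant analysis is described. A reader might infer that the trial would wrongly declare the algorithm converged or not converged. The documents contain no such rule, so the risk lies in interpretation. Nothing here touches the feasibility, acceptability or dietary conclusions. The change is worth making because it is mainly tabulation.

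**What to change.** In 2.3 and 9.2.3:

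1. Keep the 12-week share as a description. Define all shares over decision points, with 'no message' in the denominator, and word 2.3 to match the four options in 9.2.3.
2. Add shares per category by study week and by block (weeks 1-4, 5-8, 9-12), and state the length of the random start.
3. Assess convergence from within-participant change between blocks, summarised across participants. Use the size of change (for example, the absolute difference per category), because signed changes averaged over people merely reproduce the pooled share and cancel in the same way.
4. Base sub-group comparisons on weeks 9-12. If learning is shared across participants, also report by enrolment order.

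**Cost.** Wording and some extra tabulation; no new participants, visits or questionnaires. It assumes that each dated decision, including 'no message', is recorded. Section 5.1 describes scheduling, two-way messaging and a dashboard but does not say so; this should be confirmed.

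**Limits.** At one decision per day a block holds 84 / 3 = 28 decisions per participant. At a share of 0.25 the SE is √(0.1875 / 28) = 0.082, and the 95% margin for one person's change between blocks is 1.96 × √2 × 0.082 = ±0.23. A per-person stability rule would therefore be too noisy. Even a fixed policy would show an average absolute change of about √(2/π) × √2 × 0.082 = 0.09 by chance (normal approximation), so the observed average should be set against the chance value for the shares concerned. A policy that responds to recent intake may also shift weekly shares after it has settled, and the report should say so.
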